10.5. Administration

Subjects will be administered 800 mg of tazemetostat orally twice daily (approximately 12 hours apart), with or without food, at approximately the same time each day.

Tazemetostat will be administered in continuous 28-day cycles beginning on Cycle 1 Day 1 through the end of Cycle 24, for 24 months of therapy or until disease progression, unacceptable toxicity, or withdrawal of consent.

Missed or vomited dose: If a dose of tazemetostat is missed (ie, not taken within 4 hours of the scheduled dosing time), do not take the dose. Resume dose administration at the next scheduled dose. If a subject vomits after tazemetostat administration, do not take an additional dose. Resume dose administration at the next scheduled dose.

Rituximab will be administered by either subcutaneous injection or IV infusion according to the regional product prescribing information, labeling, and institutional guidelines.

For subjects receiving IV rituximab, rituximab via IV infusion will be administered at a dose of 375 mg/m² on Day 1, 8, 15, and 22 of Cycle 1, and then on Day 1 of Cycles 3 through 6, accounting for an additional 4 doses (ie, a total of 8 doses of rituximab in 6 cycles).

For subjects planning to receive subcutaneous rituximab hyaluronidase, the initial dose (Cycle 1 Day 1) of rituximab will be administered as 375mg/m² via IV infusion. Subsequent doses of rituximab may be administered via IV infusion or subcutaneously (SC) per Investigator choice. For SC rituximab hyaluronidase, administer 1,400 mg rituximab and 23,400 Units hyaluronidase (11.7 ml total volume) over approximately 5 minutes on Cycle 1 Days 8, 15, and 22 then Day 1 of Cycles 3-6, for a total of 8 doses of rituximab in 6 cycles (an initial IV rituximab dose followed by 7 doses of SC rituximab).

On days when both drugs are administered, tazemetostat should be taken prior to the dosing of rituximab.

All doses of study drugs administered, missed, and vomited (as applicable) are to be recorded.

10.6. Study Drug Accountability

In compliance with local regulatory requirements, drug supplies will not be sent to the Investigator until the following documentation has been received by the Sponsor:

- A signed and dated confidentiality agreement
- A copy of the final protocol signature page signed and dated by the Investigator
- Written proof of approval of the protocol, the informed consent form(s) (ICFs), and any other information provided to the subjects by the Institutional Review Board or Independent Ethics Committee (IRB/IEC) for the institution where the study is to be conducted
- A copy of the IRB/IEC-approved ICF and any other documentation provided to the subjects to be used in this study
- A copy of the regulatory authority approval for the country in which the study is being conducted (if required) and the import license (if required)
- An Investigator-signed and dated Form Food and Drug Administration (FDA) 1572, a signed and dated curriculum vitae for the Principal Investigator (PI) including a copy of the PI's current medical license (required in the US) or medical registration number on curriculum vitae
- Financial Disclosure Form for the PI listed on Form FDA 1572
- A signed and dated clinical trials agreement.

The Investigator and study staff will be responsible for the accountability of all clinical supplies (dispensing, inventory, and record keeping) following the Sponsor's instructions and adherence to Good Clinical Practice (GCP) guidelines as well as local and regional requirements.

Under no circumstances will the Investigator allow the study drug to be used other than as directed by this protocol. Clinical supplies will not be dispensed to any individual who is not enrolled in the study. An accurate and timely record of the receipt of all clinical supplies, dispensing of study drug to the subject, collection and reconciliation of used and unused supplies that are either returned by the subject or shipped to the site but not used, subsequent return of unused study drug to the Sponsor or designated central or local depot, and (where applicable) destruction of study drug at the site must be maintained. This includes but may not be limited to: (a) documentation of receipt of clinical supplies, (b) study drug dispensing/return reconciliation log, (c) study drug accountability log, (d) all shipping service receipts, (e) documentation of drug returned to the Sponsor, and (f) certificates of destruction for any destruction that occurs at site. All forms will be provided by the Sponsor. Any comparable forms that the investigational site wishes to use must be approved by the Sponsor.

The supplies and inventory records must be made available, upon request, for inspection by the designated representative of the Sponsor or a representative of any health authority. All used and

Protocol EZH-1401 Amendment 2.0 21 October 2021

unused study drugs, including empty containers, are to be returned to the Investigator by the subject and ultimately to the Sponsor's designated contractor or depot by the conclusion of the study, unless approval is given by the Sponsor for destruction of supplies and containers at the investigational site. Upon completion of drug accountability and reconciliation procedures by investigational site personnel and documentation procedures by the Sponsor's personnel, study drug that is to be returned to the Sponsor's approved contract vendor must be boxed and sealed and shipped back to the Sponsor's approved contract vendor following all local regulatory requirements. In some regions, study drugs may be removed from the site and hand delivered to the Sponsor's specified location by sponsor representatives.

Drug accountability will be reviewed during site monitoring visits and at the completion of the study.

10.7. Study Drug Handling and Disposal

All drug supplies are to be used only for this protocol and not for any other purpose. The Investigator (or a designated pharmacist) must not destroy any drug labels or any partly used or unused drug supply before approval to do so by Epizyme. At the conclusion of the study and as appropriate during the course of the study, the Investigator (or a designated pharmacist) will either return all used and unused drug containers, drug labels, and a copy of the completed drug disposition form to the Epizyme designated contractor or, where approval is given by Epizyme, will destroy supplies and containers at the investigational site.

11. ASSESSMENT OF EFFICACY

11.1. Tumor Assessments

Tumor response assessments will be performed (Cheson, 2014; Appendix 3) at each assessment time point and entered onto the appropriate eCRF. Investigator determined response assessments at each assessment time point will be entered onto the appropriate eCRF. All baseline local tumor assessments are to be performed within 28 days prior to the start of study treatment.

For additional details, see the Schedule of Visits and Procedures (Table 2).

Tumor response assessments at screening and during the study will include ¹⁸fluorodeoxyglucose-positron emission tomography (¹⁸FDG-PET) and computed tomography (CT), or combined as PET-CT when both imaging modalities are required, of the neck, chest, abdomen and pelvis, and other applicable sites of disease. Magnetic resonance imaging (MRI) instead of CT may be performed if clinically indicated. Additional imaging of brain or bone by MRI or CT, as appropriate, to be performed if metastases are present or suspected. All CT scans (including PET-CT and CT) must be of diagnostic quality AND preferably contrast enhanced; FDG-avid disease should report PET-CT based response, non FDG-avid disease (low or variable FDG avidity) should report CT based response. ¹⁸FDG-PET required at screening then during study treatment at 3 months (±7 days). ¹⁸FDG-PET also required at the first notation of possible CR and thereafter may be performed as clinically indicated at tumor assessment timepoints. CT required at screening then during study treatment (± 7 days) at 3 months, 6 months, 12 months, 18 months, and 24 months. If no disease progression previously documented and subject continues treatment with tazemetostat beyond 24 cycles; CT, with additional ¹⁸FDG-PET as clinically indicated, required every 6 months (±7 days). At End-of-Treatment, CT with additional ¹⁸FDG-PET required if no disease progression previously documented. During Survival Followup, tumor assessments will be performed by CT, with additional ¹⁸FDG-PET as clinically indicated, every 6 months (± 30 days) for 2 years then every 12 months (± 30 days) thereafter, or until disease progression.

CT (or MRI if clinically indicated) scans are considered the primary and preferred method of response assessment, with ¹⁸FDG-PET additionally required at certain time points.

A standard-of-care clinical examination for lymphoma, including assessment of B symptoms, will be performed at screening and with tumor assessments. A bone marrow biopsy (including immunohistochemistry [IHC]) will be performed for those subjects at screening with a history of lymphoma involvement of the bone marrow if a bone marrow biopsy with IHC has not been performed within 42 days of cycle 1 day 1. A written approval from the Medical Monitor is required if the bone marrow biopsy with IHC is performed outside of the allowed protocol-specified window. At the first notation of possible CR and when clinically indicated, a repeat bone marrow biopsy should be performed if lymphoma involvement of the bone marrow was reported at screening. If bone marrow biopsy is not performed at CR, ¹⁸FDG-PET will be used to confirm CR (Perry, 2016; Rutherford, 2017).

All subjects will be followed until disease progression as indicated in the Schedule of Assessments (Table 2). Subjects who discontinue study treatments for any reason other than withdrawal of consent or disease progression without documented evidence of disease progression, i.e., if a subject withdraws consent but agrees to continue collection of follow-up

Protocol EZH-1401 Amendment 2.0 21 October 2021

data, will continue to be assessed as scheduled until disease progression. For equivocal progression, the Investigator is strongly encouraged to contact the Medical Monitor for evaluation in a real-time manner.

11.2. Techniques

The CT scan should be a diagnostic quality spiral or multidetector CT with oral and iodinated intravenous (IV) contrast, and the MRI scan should be performed with IV gadolinium chelate. Scans of the neck, abdomen, pelvis, and other areas of the body may be performed with MRI instead of CT, but evaluation of the chest must be done with CT. If iodinated IV contrast is contraindicated, the chest evaluation should be done with non-contrast CT, and the abdomen and pelvis evaluation should be performed using either CT with oral contrast (without IV contrast) or MRI with gadolinium chelate IV contrast (the latter is preferred). Spiral/multidetector CT should be performed with a 5-mm contiguous slice reconstruction algorithm. If body MRI scans are performed, contiguous slices of 5 mm are also recommended.

The same imaging modality and image-acquisition protocol (including use or nonuse of IV contrast) should be used consistently across all time points to allow consistent comparison of lesions. Low-dose noncontrast CT transmission scans from a positron emission tomography-CT (PET-CT) combination scanner are not acceptable, unless they are of diagnostic quality. Ultrasound should not be used for radiographic tumor assessment.

Brain scans should be performed by MRI pre- and post-contrast enhancement or CT with contrast enhancement, with 5-mm contiguous slices recommended (maximum inter-slice gap of 1 mm on MRI).

Whole body ¹⁸FDG-PET scans should be performed using institutional guidelines.

If subcutaneous masses or nodes are palpable (eg, bulky) and are assessable by both clinical and radiographic techniques, the radiographic (CT or MRI) technique should be used for the assessment of target and nontarget lesions.

Assessments are to be performed at the site by appropriately qualified personnel and results of the site interpretation are to be recorded on the appropriate eCRFs.

11.3. Independent Review Committee

An IRC review will be used, if the data are promising and warrants label expansion for tazemetostat, to decrease any potential bias of Investigator assessments of radiologic response. The IRC will be chartered to evaluate response assessment for analysis independently per 2014 Lugano Classification (Appendix 3). Blinded reviewers will be radiologists experienced in oncology. The independent review will not be used for treatment decisions. Investigators will review for standard of care.

11.4. Survival Follow-up

Survival follow-up will be conducted approximately every 90 days on all subjects, unless subject withdraws consent. Information on all anticancer therapies will be collected (the Sponsor may choose to stop the collection of therapies after the first anticancer treatment following tazemetostat). This may be done by telephone contact. Once the study has achieved the number of events necessary for the final analysis, subjects may no longer be contacted for this information.

12. ASSESSMENT OF SAFETY

Safety assessments will consist of monitoring and recording of all AEs, including all Common Terminology Criteria for Adverse Events (CTCAE V5.0).

For details, refer to the Schedule of Visits and Procedures (Table 2).

12.1. Safety Parameters

12.1.1. Demographic/Medical History

Demographic information will be collected at the Screening Visit. Standard demography parameters include age, gender, and race/ethnicity (recorded in accordance with prevailing regulations). The Screening Visit will occur within 28 days prior to the first dose of study drug to confirm that the subjects meet the selection criteria for the study. The assessments to be conducted at screening are provided in Table 2 (Schedule of Visits and Procedures). Medical and surgical histories will be obtained at the Screening Visit, along with a record of prior concomitant medications and/or procedures. Significant findings before the start of study drug will be recorded on the Medical History and Current Medical Conditions eCRF. A standard of-care clinical examination for lymphoma, including assessment of B symptoms, will also be performed at the Screening Visit and at all disease assessments.

12.1.2. Vital Signs

Vital signs will be collected at the visits designated in the Schedule of Visits and Procedures (Table 2) by a validated method. Vital sign measurements will include systolic and diastolic blood pressure, heart rate (beats per minute), and body temperature (°C). Blood pressure and heart rate will be collected after subjects have been sitting for 5 minutes.

When vital signs are to be obtained concurrently with blood samples, the vital sign measurements will be performed before blood samples are collected in order to maximize the accuracy of blood sampling times while minimizing the potential effects of blood collection on other safety assessments.

12.1.3. Weight and Height

Body weight (kg) is required to be measured at the visits designated in the Schedule of Visits and Procedures (Table 2). Height measurement is required at the Screening Visit only.

12.1.4. Eastern Cooperative Oncology Group Performance Status

An ECOG performance status assessment will be completed at the visits designated in the Schedule of Visits and Procedures (Table 2). The ECOG performance scale will be used (Appendix 1).

12.1.5. Physical Examinations

12.1.5.1. Comprehensive Physical Examination

A comprehensive physical examination of all body systems must be performed by a qualified licensed individual at the visits designated in the Schedule of Visits and Procedures (Table 2). A review of body systems will include the following:

- General appearance
- Skin
- Head, ears, eyes, nose, throat
- Respiratory
- Cardiovascular
- Abdomen (including liver and kidneys)
- Neurological examination with sensory testing and seizure status, if applicable
- Musculoskeletal

Any abnormalities or changes in intensity noted during the review of body systems should be documented in the source document and reported appropriately in the eCRF. If a new clinically significant finding (e.g., not noted at screening) occurs from the initial tazemetostat administration until the end of the study, an AE must be documented. In addition, resolution of any abnormal findings during the study will be noted in source document and the eCRF if clinically significant.

12.1.5.2. Symptom-Directed Physical Examination

A symptom-directed physical examination must be performed by a qualified licensed individual at visits where a comprehensive PE is not required for that visit (Table 2). This will consist of a focused review of systems and physical examination addressing any new symptoms, AEs, or complaints.

12.1.6. Laboratory Assessments

Clinical laboratory samples will be collected at the visits designated in the Schedule of Visits and Procedures (Table 2). The clinical laboratory parameters that will be measured are detailed in Table 7.

All routine, scheduled clinical laboratory assessments and screening laboratory assessments (see below) will be conducted locally only (these samples should not be sent to central laboratory for testing unless local testing is not available):

- Hematology
- Comprehensive chemistry panel
- Lactate dehydrogenase(LDH)
- Peripheral blood smear (Section 12.1.8)

- Cytogenetic testing and, if necessary, DNA sequencing by NGS of bone marrow aspirate/biopsy for subjects with abnormal morphology in peripheral blood smear suggestive of MDS/AML or MPN (performed by local laboratory, please refer to Lab Manual for details. Please see below if local laboratory is not equipped.)
- Viral serology/virology (Section 12.1.7)
- Pregnancy testing (serum or urine as indicated) (Section 12.1.9)
- The below samples/assessments may be conducted at the appropriate central laboratory:
 - If local laboratory is unable to perform cytogenetic testing and, if necessary, DNA sequencing of prespecified disease-related genes by NGS, or if results are inconclusive/indeterminate: bone marrow aspirate/biopsy for subjects with abnormal morphology in peripheral blood smear suggestive of MDS/AML or MPN can be sent to central laboratory for testing as backup.

NOTE: In the future, any of the blood and tissue samples that were not completely used may be used for additional research.

A Laboratory Manual will be provided to detail handling, processing, and shipping procedures.

All hematology and serum chemistry (including pregnancy testing, where applicable) samples are to be obtained before study drug administration and results reviewed before administration/dispensing of study drugs. For the management of clinically significant laboratory abnormalities, refer to the dose adjustment criteria for tazemetostat in Section 7.4.1.

A laboratory abnormality may meet the criteria of an AE as described in this protocol (Section 12.2.1.1) and the eCRF completion guidelines. In these instances, the AE corresponding to the laboratory abnormality will be recorded on the Adverse Event eCRF.

For a laboratory abnormality meeting the criteria for an SAE (Section 12.2.1.2), the study site must send the SAE reporting form and the laboratory report to the Sponsor or Sponsor's designee at the fax number or email address indicated in the Investigator file.

Table 7: Clinical Laboratory Tests

Category	Parameters
Hematology	hematocrit, hemoglobin
	red blood cell count
	• platelet count
	• white blood cell count with differential and ANC (neutrophils, bands [optional], basophils, eosinophils, lymphocytes, and monocytes,)
	• peripheral blood smear morphology assessment (if peripheral blood smear morphology is abnormal and suggestive of MDS/AML or MPN, then conduct bone marrow aspirate/biopsy with cytogenetic testing to closely monitor subjects for cytogenic abnormalities known to be associated with myelodysplastic syndrome [MDS; eg, del 5q, chr 7, abn] and myeloproliferative neoplasm [MPN; eg, JAK2 V617F]. Additional testing of genetic aberrations associated with MDS/AML or MPN can be conducted using targeted next generation sequencing (NGS) of known disease genes, as necessary.)
	• Complete blood count with peripheral blood smear will be performed at least once every 3 months while a subject is receiving tazemetostat.
Chemistry	
Comprehensive	• bicarbonate
Metabolic	• chloride
(Chemistry) Panel	• potassium
	• sodium
	• alkaline phosphatase (ALP),
	• alanine aminotransferase (ALT),
	• aspartate aminotransferase (AST),
	• total bilirubin,
	• albumin
	• calcium,
	• glucose,
	• total protein,
	blood urea or blood urea nitrogen,
	• creatinine
Other	• lactate dehydrogenase(LDH)

12.1.7. Viral Serology/Virology

If infection status is unknown at screening, testing should include viral serologies for HBV (Appendix 7) and HCV (Appendix 8), and virology testing for HBV and HCV (as indicated), and HIV as per institutional standard. Additional HBV-DNA testing by PCR may be required if subject is HBsAg negative, anti-HBs positive and/or anti-HBc positive. Hepatitis C virus testing by HCV antibody and if positive (reactive), further HCV-RNA testing by PCR must be performed.

12.1.8. Bone Marrow Aspirate/Biopsy Pertaining to AESI

At screening and during the study, a peripheral blood smear will be performed manually or automated along with routine hematology testing and assessed for abnormal morphology. If results are abnormal and suggestive of MDS/AML or MPN, the subject will undergo a bone

Protocol EZH-1401 Amendment 2.0 21 October 2021

marrow aspirate/biopsy procedure. The bone marrow aspirate/biopsy sample will then be analyzed by cytogenetic testing at the local laboratory to closely monitor subjects for abnormalities known to be associated with MDS (e.g., del 5q, chr 7, abn) and MPN (e.g., JAK2 V617F). Additional local laboratory testing of genetic aberrations associated with MDS/AML or MPN can be conducted using targeted next generation sequencing (NGS) of known disease genes, as necessary. If local testing is unavailable or if results are inconclusive/indeterminate, the site will be required to ship samples for central laboratory testing. If the cytogenetic testing and, if conducted, DNA sequencing by NGS results are abnormal and associated with myeloid malignancies, tazemetostat will be discontinued.

12.1.9. Pregnancy Testing

A serum pregnancy test (β -hCG) must be performed at Screening and within 24 hours prior to the first dose of study drug for all FCBP. Subsequent pregnancy testing will be performed predose on Day 1 of each cycle beginning with Cycle 2 and at the End-of-Treatment visit by urine or serum. Pregnancy tests will have a minimum sensitivity of 25 mIU/mL. Any positive urine pregnancy test must be confirmed by a serum test. Blood (or urine) will be collected for pregnancy testing at designated time points on the Schedule of Visits and Procedures (Table 2).

Refer to Section 12.4.2 for reporting of pregnancy.

12.2. Adverse Events

12.2.1. Definition of Adverse Events

12.2.1.1. Adverse Events

An AE is any untoward medical occurrence in a subject or clinical investigation subject administered an investigational product. An AE does not necessarily have a causal relationship with the investigational product. An AE can therefore be any unfavorable and unintended sign (including an abnormal laboratory finding), symptom, or disease temporally associated with the use of an investigational product, whether or not related to the investigational product.

Laboratory values that are deemed not clinically significant or related to underlying disease do not need to be captured as AEs. Laboratory values that warrant treatment change or result and an SAE do need to be captured as applicable.

Events that do not meet the definition of an AE include:

- Medical or surgical procedure (eg, endoscopy, appendectomy); the condition that leads to the procedure is an AE
- Situations where an untoward medical occurrence did not occur (social and/or convenience admission to a hospital)
- Anticipated day-to-day fluctuations of pre-existing disease(s) or condition(s) present or detected at the start of the study that do not worsen

All AEs will be collected from time of signing informed consent to 30 days after the final dose of study drug, or until the start of subsequent anticancer therapy, whichever happens first. If subject is unable to return to the clinic for assessment of AEs this may be done by [contact]. Serious Adverse Events

A SAE is any adverse event (untoward medical occurrence) that at any dose:

- Results in death
- Is life-threatening (ie, the subject was at immediate risk of death from the AE as it occurred; this does not include an event that, had it occurred in a more severe form or was allowed to continue, might have caused death)
- Requires inpatient hospitalization or prolongation of existing hospitalization
- Results in persistent or significant disability/incapacity, or
- Is a congenital anomaly/birth defect (in the child of a subject who was exposed to the study drug)
- Other important medical events that may not be immediately life-threatening or result in death or hospitalization, but when based on appropriate medical judgment, may jeopardize the subject or may require intervention to prevent one of the outcomes in the definition of an SAE listed above should also be considered SAEs. Medical and scientific judgment should be exercised in deciding whether expedited reporting is appropriate in such situations.

The following hospitalizations are not considered to be SAEs because there is no "AE" (ie, there is no untoward medical occurrence) associated with the hospitalization:

- Hospitalizations for respite care
- Planned hospitalizations required by the protocol
- Hospitalization planned before informed consent (where the condition requiring the hospitalization has not changed post study drug administration)
- Hospitalization for administration of study drug or insertion of access for administration of study drug
- Hospitalization for routine maintenance of a device (eg, battery replacement) that was in place before study entry
- An emergency room visit lasting longer than 24 hours but not resulting in hospitalization

Note: Disease progression is a study endpoint and should not be reported as an SAE term. However, AEs (eg, dyspnea) that meet seriousness criteria, although associated with disease progression, should be reported as an SAE. Refer to Section 12.2.3.

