12.3.1. Assessing Severity of Adverse Events

Adverse events will be graded on a 5-point scale according to CTCAE V5.0 (Appendix 2). Investigators will collect all CTCAE grades for AEs (for both increasing and decreasing severity). All AEs reported using CTCAE classification and graded as 4 or 5 are to be considered serious. Every effort must be made by the Investigator to categorize each AE according to its severity and its relationship to the study drug. In the event that an AE is not covered by the CTCAE, the assessment of severity will be determined by using the CTCAE general guidelines.

Grade 1	Mild: asymptomatic or mild symptoms; clinical or diagnostic observations only; intervention not indicated.
Grade 2	Moderate: minimal, local, or noninvasive intervention indicated; limiting age- appropriate instrumental activities of daily living (ADL).
Grade 3	Severe or medically significant but not immediately life-threatening: hospitalization or prolongation of hospitalization indicated; disabling; limiting self-care ADL.
Grade 4	Life-threatening consequences: urgent intervention indicated.
Grade 5	Death related to AE.

An AE that is assessed as severe should not be confused with an SAE. Severity is a category used for rating the intensity of an event (as in "mild," "moderate," or "severe"). See Section 12.2.1.2 for the definition of an SAE.

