14.7. Criteria for Early Stopping Due to Unacceptable Rates of Adverse Events

Criteria will be in place for halting enrollment and treatment due to safety findings:

- Any fatality that is at least possibly related to treatment calls for immediately stopping accrual and treatment. If attribution is in doubt, the study should be halted until attribution is definitively determined and a decision is made by the study team.
- Two or more observations of a secondary myelodysplastic syndrome or AML or secondary malignancy attributed to tazemetostat will result in stopping accrual and treatment. (Note: observations may not occur during the study period and may occur later, after it is too late to stop accrual.)
- Continuous monitoring with Pocock-like boundaries using the method of Ivanova (Ivanova, 2005) will be utilized for other categories of adverse events, with following rates applied to the continuous stopping rules:
- Combined rate of reportable SAE or SUSAR: 10%
 - Any single category of grade > 3 AE: 50%
 - Grade >3 non-hematologic AE overall: 30%

A table of stopping boundaries for these criteria are provided in Appendix 5. These criteria are independent of the futility analysis for efficacy and will be applied to all subjects that receive any treatment with tazemetostat, regardless of mutation status. See Appendix 2 for details. The stopping rules assume a full accrual of 54 subjects in order to retain statistical properties.

However, if the study stops early due to futility, any bias introduced in the stopping rules due to a change in total accrual should no longer be a concern.

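### Section 12.2.1.2 treats an emergency room stay of more than 24 hours as if no adverse event lay behind it, so a medically important event of Grade 3 or lower can be left out of the SAE count

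*Protocol*

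**What the plan says.** Protocol Section 12.2.1.2 defines an SAE by outcome. One criterion is the setting of care: "Requires inpatient hospitalization or prolongation of existing hospitalization". Another needs no admission and rests on medical judgment: "Other important medical events that may not be immediately life-threatening or result in death or hospitalization" still qualify if they "may jeopardize the subject or may require intervention to prevent one of the outcomes in the definition of an SAE listed above".

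The exclusion list comes straight after. It opens with "The following hospitalizations are not considered to be SAEs because there is no" AE, and explains this as meaning that "there is no untoward medical occurrence) associated with the hospitalization". Five items follow that concern respite care, stays the protocol requires, stays planned before consent, giving study drug or placing access for it, and device upkeep. The sixth is "An emergency room visit lasting longer than 24 hours but not resulting in hospitalization". It carries no qualifier.

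Two other places matter. Section 12.3.1 adds a rule by grade: "All AEs reported using CTCAE classification and graded as 4 or 5 are to be considered serious". Section 14.7 makes SAEs the input to a continuous stopping boundary, with the reference rate given as "Combined rate of reportable SAE or SUSAR: 10" (per cent).

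**The concern.** The first five items share the stated reason: each is a stay that happens without a new medical event. An emergency room visit of more than a day does not share it. People stay that long because something has gone wrong, and that something is an adverse event under Section 12.2.1.1.

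Because the item is unqualified and follows the important-medical-event criterion, a site can read it as a specific exception to that general rule. An event the investigator would otherwise have called serious is then not sent to the sponsor within one business day (Section 12.4), is not counted in the SAE part of the secondary safety endpoint, and does not enter the SAE/SUSAR boundary. The error has one direction: it can remove SAEs but cannot add any.

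**Working it through.** No figure in the plan belongs to this item, so the main check is to set the passages side by side.

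**Step 1. Does the item fit its heading?** The heading covers hospitalizations with no AE. The item says that no hospitalization resulted, and it says nothing about the cause of the visit. It fails both parts of the heading.

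**Step 2. Which events could it remove?** Take an event managed in an emergency room stay of more than 24 hours, without admission.

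| Event | Route to SAE handling without admission | Exposed to the item? |
|---|---|---|
| Fatal, life-threatening or disabling | Own criteria, Section 12.2.1.2 | No |
| Grade 4 or 5 | Serious by grade, Section 12.3.1 | No |
| Adverse event of special interest | SAE reporting procedures, Sections 12.2.2 and 12.4.1 | No |
| Grade 3 or lower, medically important | Important-medical-event criterion, by judgment | **Yes**, on a literal reading |
| Grade 3 or lower, not judged medically important | None | No: not an SAE with or without the item |

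The gap is the fourth row. It is not empty, because Section 12.3.1 describes Grade 3 as severe or medically significant, with hospitalization indicated. A Grade 3 event handled in a long emergency room stay is the natural case.

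**Step 3. Would another boundary catch it?** The two grade-based boundaries in Section 14.7 (50% for any single category, 30% for non-hematologic events overall) do not depend on SAE status, but are printed as Grade >3. Read literally, a Grade 3 event counts toward neither. If Grade 3 or higher is meant, it would count there.

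**Step 4. How much could the SAE boundary lose?** This is an illustration only. The table in Appendix 5 is not in the text available for this review, the overall crossing probability is not stated, and no document gives a missed share.

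- From Section 14.7: N = 54, reference rate 10%, Pocock-like continuous monitoring.
- Assumed: overall crossing probability at a true rate of 10% of 0.05 or 0.10; missed share f of SAE subjects from 0 to 20%.
- Boundary: after n subjects, stop at the smallest k with P(Bin(n, 0.10) ≥ k) ≤ a, where a is the largest pointwise level that keeps overall crossing within the target. This gives a = 0.0128 (attained 0.0487, 12 subjects at n = 54) and a = 0.0282 (attained 0.0990, 11 subjects at n = 54).
- Thinning: a true rate p is seen as p(1 − f); for example 0.20 × 0.90 = 0.18. Crossing probabilities are exact.

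| True SAE rate | Assumed overall level | f = 0 | f = 5% | f = 10% | f = 20% |
|---|---|---|---|---|---|
| 20% | 0.05 | 0.573 | 0.506 | 0.437 | 0.303 |
| 20% | 0.10 | 0.697 | 0.636 | 0.571 | 0.432 |
| 30% | 0.05 | 0.961 | 0.937 | 0.904 | 0.799 |
| 30% | 0.10 | 0.980 | 0.967 | 0.947 | 0.876 |
| 42% | 0.05 | 1.000 | 0.999 | 0.998 | 0.989 |
| 42% | 0.10 | 1.000 | 1.000 | 0.999 | 0.995 |

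The 42% is the program's own adult rate of treatment-emergent SAEs (Section 5.2.2: 326 of 779). At that rate, with 20% missed, the observed rate is 0.42 × 0.80 = 0.336 and the boundary is still crossed with probability of at least 0.98. Under-capture would matter for stopping only if the true rate were much lower, nearer 20%.

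**The case against.** The strongest reply is that the list concerns hospitalizations only. On that view the item says merely that a long emergency room stay does not by itself meet the inpatient criterion, and it leaves every other criterion standing. Section 12.2.1.1 also has all AEs collected from consent to 30 days after the last dose, so the event stays in the treatment-emergent AE part of the same endpoint.

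Much of this stands, and it rules out several stronger readings.

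- A reader might infer that acute toxicity treated without admission is generally left out of the SAE endpoint and boundary. The documents do not support that: four of the five rows in Step 2 are unaffected.
- A reader might infer that sites are told to record no AE. The wording invites this, since Section 12.2.1.1 uses nearly the same phrase for situations that are not AEs. But the AE definition and the collection rule in that section point the other way.
- A reader might object that two subjects with the same event are counted differently because only one was admitted. That follows from the inpatient criterion itself and would remain after the item is deleted.
- A reader might say the 24-hour threshold runs the wrong way. The documents give no reason for the threshold, so that is a guess about intent.

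What the reply does not remove is the conflict. The text does not say that the visit fails one criterion; it says such cases are not SAEs and have no AE behind them. A neighboring item, on stays planned before consent, carries a condition and this one does not. The sensible reading has to be supplied by the site.

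**Conclusion.** The item contradicts its own heading and conflicts with the important-medical-event criterion; that is certain from the text. The consequence is narrow: a medically important event of Grade 3 or lower, managed in a long emergency room stay, can be left out of SAE reporting and the 10% SAE/SUSAR count by a site that applies the item literally.

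The size cannot be derived. The missed share and the boundary in Step 4 are assumptions, so the fall from 0.573 to 0.437 (true rate 20%, 10% missed, level 0.05) is an example and not an estimate of lost sensitivity. Nor can a share be taken off the 42%, because the documents do not say which exclusions applied in the studies behind it.

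The practical effect is now small. The SAP (Sections 5.2 and 8) reports early termination with 5 treated subjects and no futility or efficacy analysis, and its AE output (Section 10.1) is listings only. Those listings do include all SAEs and treatment-emergent SAEs, and one misclassified subject would be 1/5 = 20% of those treated.

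**What to change.** Delete the emergency room item from the exclusion list in Section 12.2.1.2. State in its place that the AE behind an emergency room stay is always recorded and is judged against all seriousness criteria, including medical importance. Before the SAE listings in SAP Section 10.1 are finalized, check the 5 treated subjects for such stays and confirm how the underlying events were classified.

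The cost is one line of text, a check of five records and possibly a few more SAE reports. No analysis changes.
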